### 6.1.2 DOSING AND ADMINISTRATION

Each subject will have their tinnitus spectrum assessed with the Tinn Tester protocol (L. Roberts et al, 2008). This spectrum is digitized and programmed into the device as the signal to be delivered to the subject. The amplitude is limited to 95 dB SPL and is delivered together with an electrical stimulus delivered a short time after the auditory stimulus (as determined by the preclinical studies). This stimulus is presented by the device when the subject turns on the device. The device limits the time of presentation to 30-60 min per day.

This protocol is presented once a day for 30-60 minutes for 6 weeks. After that there is a washout period of 6 weeks in which no device is used. Subjects are tested once a week to assess the primary and secondary outcomes and when baseline is achieved. The second arm of the study begins for another 6 weeks. A second washout of 6 weeks occurs, end of study visit, and 12 weeks of follow up, after which the subject participation is ended. Completion of Arm 1 and Arm 2 do not necessarily have to be consecutive, and we will allow for 12 weeks in between in order to provide more flexibility for subjects. The dose will not change over the course of the study. Maximum duration of enrollment is 36 weeks.

The subjects will be trained on how to use the devices and place the earphones and electrode pads. Once they have been effectively trained, subjects will take the devices home to use for the 30-60 min/day periods. Once a week the primary and secondary outcomes will be tested along with any review or questions that the subjects need to be answered. Subjects are asked to use the device at the same time every day but If subjects miss a treatment they are instructed to use it at another time rather than miss that treatment.

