### 6.3 MEASURES TO MINIMIZE BIAS: RANDOMIZATION AND BLINDING

Subjects are randomly assigned to group 1 (active first, then sham) or group 2 (sham first, then active) using Matlab's *randsample* command with a predetermined, fixed, secret seed value. *Randsample* generates random numbers using the Mersenne twister algorithm. We will enroll subjects in a 1:1 ratio to create a balanced study design. To ensure blinding, group assignment is generated *in silico* and assignment programmed into each device, without the intervention of a study member. This parameter is not made accessible to study members without password authorization. Devices are encrypted to prevent study team members or subjects from accessing device data in an unauthorized manner.

As the randomization list is generated algorithmically, the code can be reproduced with knowledge of the secret seed value. Unblinding may occur at the end of the study or in the case of an SAE related to the study (worsening of tinnitus, worsening of hearing threshold). Study investigators that do not have contact with subjects may unblind. Intentional and unintentional unblinding must be reported to the principle investigator.

Imperfect blinding could arise from the presence of the electrical stimulation present during active treatment. To avoid unblinding, subjects will be told that they may or may not feel electrical stimulation during both phases of the study. The previous study suggested that subjects tend to acclimate to the presence or lack of electrical stimulation during a day's treatment. Subjects will be discouraged from divulging whether they can feel the electrical stimulus.

No investigators are allowed to remain unblinded for the duration of the study. All analyses that could require unblinding (SAEs, worsening of a subject's tinnitus/hearing) will be identified by software, and the investigators notified by automated communication methods.

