### 6.4 STUDY INTERVENTION COMPLIANCE

The devices are electronic monitoring compliant – successful daily use is registered, also detects and records open circuits or failures. Primary and secondary outcomes are measured weekly and recorded by study team members electronically on secure databases.

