## 9.3 POPULATIONS FOR ANALYSES

All subject's data will be analyzed in one cohort. We will perform both per-protocol and intention-to-treat analyses. While intention-to-treat analysis is ideal, our protocol may require subjects to adhere to a strict schedule in order to fully realize the benefit of the treatment. Our pilot study had excellent compliance rates, but a longer and larger study provides more opportunity for non-compliant subjects. Should sensitivity analysis between the intention-to-treat and per-protocol analyses attain significance, differences between compliant and non-compliant subjects will be further explored in an effort more fully understand who best can benefit from the bimodal protocol. Missing data and losses to follow-up will be managed using

a last observation carried forward approach. Sensitivity analysis to outliers will also be performed. If results differ significantly between with and without outliers, outliers will be further investigated to determine what factors impact the likelihood of a subject responding or being resistant to the treatment protocol.

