### 9.4.1 ANALYSIS OF THE PRIMARY EFFICACY ENDPOINT(S)

For all endpoints (Tinnitus loudness, TFI and THI), the following approach will be utilized. All measures are ordinal, repeated measures. Final analysis will occur after unblinding.

Tinnitus loudness is measured by having subjects match the loudness and likeness of their tinnitus to one of 11 sounds with different center frequencies. Absolute differences are averaged relative to baseline to determine loudness. TFI and THI are questionnaires to be completed at each weekly visit. Both are measured on an interval scale. See section 3.1 for more details

A General Linear/Logistic Mixed (GLLM) effects analytic model will be used. GLLM is considered ideal when analyzing repeated measures as it treats time as a continuous variable and can account for missing data. This framework can readily adapt to subgroupings present in the data. GLLM analysis includes random and fixed effects. In this study, treatment order (active first vs sham first), treatment condition (active, active washout, sham, sham washout), baseline loudness, baseline TFI, and interaction of treatment and treatment order are treated as fixed while intercept is treated as a random effect.

Adjustments for Type I error over the set of endpoints is unnecessary as the measures are not directly related.

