### 9.4.2 ANALYSIS OF THE SECONDARY ENDPOINT(S)

The following analytical framework will be applied to 2ndary measures (see section 3.2 for more details). Analyses are not dependent on primary-measures. All measures are ordinal, repeated measures. Data will be analyzed using repeated-measures ANOVA, and shown as mean+/-SEM. Normality will be assessed using Kolmogorov-Smirnoff tests, and non-parametric tests used for non-normally distributed data. To assess how the secondary measures might co vary with the primary measures, we will use principal component analysis or linear fixed effects models.

Non-compliant and missing data points will be excluded from analysis.

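### Section 9.4.2 drops non-compliant and missing data from the secondary endpoints, contradicting 9.3, with no rule on which section governs and no definition of non-compliance

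*Combined protocol and SAP*

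**What the plan says.** Section 9.4.2 sets one framework for the three secondary endpoints. The method is given as "Data will be analyzed using repeated-measures ANOVA", with non-parametric tests where normality fails. The section ends: "Non-compliant and missing data points will be excluded from analysis". It describes no version that keeps those data.

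Section 9.3 covers the whole trial. It puts all subjects in one cohort and says "We will perform both per-protocol and intention-to-treat analyses". It plans a comparison of the two, assigns missing data and losses to follow-up to last observation carried forward (LOCF), and anticipates that "a longer and larger study provides more opportunity for non-compliant subjects". None of this is restricted to the primary endpoints.

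Section 9.4.1, for the primary endpoints, contains no exclusion. It uses a mixed model on the ground that "GLLM is considered ideal when analyzing repeated measures as it treats time as a continuous variable and can account for missing data".

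On compliance, 6.1.2 says "This protocol is presented once a day for 30-60 minutes for 6 weeks" and 6.4 says of the device that "successful daily use is registered". No section says how much use counts as compliant.

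**The concern.** Device use and attendance happen after randomisation. Someone who feels no benefit may use the device less, and someone who can tell active from sham may use it differently in the two periods. Section 6.3 accepts the second possibility: "Imperfect blinding could arise from the presence of the electrical stimulation present during active treatment". Once those data are removed, the contrast compares the conditions among data that survived a selection which treatment may itself have influenced. It is then no longer an estimate of the effect of being assigned to active rather than sham.

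The open definition adds a second problem. Without a threshold, the excluded set could be settled after unblinding. An analyst following 9.3 and one following 9.4.2 would report different results for the same endpoint, each with the plan's support.

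At stake are the estimates for three declared efficacy endpoints.

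**Working it through.** **1. The two sections side by side (secondary endpoints)**

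| Question | 9.3 | 9.4.2 |
|---|---|---|
| Non-compliant data | Kept under intention to treat, with per-protocol alongside | Dropped |
| Missing data | Last value carried forward | Dropped |
| Threshold for non-compliance | None | None |
| Which section governs | Not stated | Not stated |

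The conflict covers both population and missing data.

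**2. The plan's own figure.** Section 9.2 requires 17 per arm for TFI, and 2 × 17 = 34 reproduces the stated total. The 17 itself cannot be checked, because the slopes and variances behind it are not given. No sample size is stated for any secondary endpoint, so this figure does not test the point.

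**3. What changes in the estimate.** Suppose a share c of active-arm data is non-compliant and carries no effect. The all-randomised contrast is (1 − c) times the effect in compliers, so the contrast after exclusion is 1/(1 − c) times the all-randomised one: 1/0.9 = 1.11, 1/0.8 = 1.25 and 1/0.7 = 1.43 for c = 10%, 20% and 30%.

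**4. What happens to power.** The documents give no non-compliance rate, effect size or correlation for these endpoints, so all of the following are assumptions: 50 subjects, paired active-sham contrast, effect 0.5 SD, within-subject correlation 0.5, two-sided 0.05, non-compliance q of 10%, 20% or 30% per arm. The SD of the paired difference is √(2 × (1 − 0.5)) = 1. Exclusion is taken to remove any subject lacking either arm. Complete pairs are 50 × (1 − q)² if non-compliance is independent between arms and 50 × (1 − q) if the same subjects are non-compliant in both. Power is by simulation.

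| Pattern | q | Pairs left | Power, exclusion | All kept, non-compliers gain nothing | All kept, half the benefit | All kept, full benefit |
|---|---|---|---|---|---|---|
| Independent | 10% | 40.5 | 87% | 87% | 91% | 93% |
| Independent | 20% | 32 | 78% | 78% | 87% | 93% |
| Independent | 30% | 24.5 | 65% | 66% | 83% | 93% |
| Same subjects | 10% | 45 | 91% | 87% | 91% | 93% |
| Same subjects | 20% | 40 | 87% | 78% | 87% | 93% |
| Same subjects | 30% | 35 | 82% | 66% | 83% | 93% |

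Under independence, exclusion gains essentially nothing and can lose. With the same subjects non-compliant in both arms and no benefit to them, it gains about 4, 9 and 16 points. If they keep half the benefit, the two approaches are within 2 points.

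**5. Bias with no true effect.** If poor responders stop using the active device only (correlation of 0.3 or 0.5 between compliance and improvement), type I error after exclusion is 5% to 9% at within-subject correlation 0.5, and up to 11% at 0.3. If stopping is equally outcome-related in both arms, it stays at about 5%. The all-data test stays near 5% throughout.

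**The case against.** The strongest reply is that 9.3 already supplies the intention-to-treat analysis. It is the populations section for the whole trial, and 9.4.2 does not switch it off. That stands: a reader might infer from 9.4.2 that the plan has no all-randomised analysis of these endpoints, and the documents do not support that. What remains is the contradiction. The endpoint-specific sentence is the one an analyst is likely to follow, and nothing says that it yields to 9.3.

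Second, 9.4.2 drops data points, not subjects, and compliance may not mean device use alone. Section 6.4 links it to logged use, while 9.3 speaks of keeping to the schedule, which could include visits. Nor does 9.4.2 specify the classical form of ANOVA that needs every cell. Loss of whole subjects is therefore an assumption of the power table.

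Third, a reader might infer that exclusion always costs power, by as much as 28 points (93% − 65%). That figure needs 30% non-compliance, independence between arms and full benefit in people who did not use the device as planned. With the same subjects non-compliant in both arms, the worst loss shown is about 12 points before rounding, and exclusion can gain. Setting the 32 remaining pairs against 34 would also be wrong: 34 is two groups of 17 for TFI, and 32 complete pairs place 32 subjects in each condition. Moreover, 7.2 withdraws subjects for significant non-compliance and replaces treated withdrawals, and up to 100 may be randomised, so 50 is not a fixed starting number.

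Fourth, the type I inflation needs outcome-related stopping confined to the active arm. Section 6.3 makes arm recognition possible, but 8.2 describes a sham with equal electrical and acoustic levels. The documents do not show that such stopping will occur, and they do not rule it out.

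**Conclusion.** The point holds as an unresolved contradiction with a real consequence. Sections 9.3 and 9.4.2 give incompatible rules on population and missing data for bandwidth, minimum masking level and the Tinnitus Hearing Survey, with no order of precedence and no definition of non-compliance. Followed as written, 9.4.2 conditions the active-sham contrast on post-randomisation behaviour, so the result cannot be read as the effect of assignment. It can be biased if stopping relates to outcome differently in the two arms.

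The size cannot be fixed from the documents. At assumed non-compliance of 10% to 30%, and no effect in non-compliers, the excluded-data contrast is 1.11 to 1.43 times the all-randomised one. Power may be unchanged, lower or higher, depending on whether non-compliance clusters in the same subjects and how much benefit they keep. The case rests on what is estimated, not on power.

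The matter is confined to secondary endpoints. The primary intention-to-treat analyses of loudness, TFI and THI are not affected. It should be corrected before unblinding.

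**What to change.** - **Section 9.4.2, population.** Delete the exclusion sentence. Make the main secondary analysis an intention-to-treat analysis of all observed data from all randomised subjects, whatever their device use.
- **Section 9.4.2, model.** Use a mixed model of the 9.4.1 type, with each endpoint's own baseline as covariate; 9.4.1 adjusts only for baseline loudness and TFI. For the three-category bandwidth measure use an ordinal or multinomial form.
- **Missing data.** State one rule for these endpoints: model-based on observed data, replacing both LOCF and exclusion. This rests on a missing-at-random assumption, which matters because subjects withdrawn under 7.2 contribute only data collected before withdrawal.
- **Section 9.3.** Move the compliance exclusion to the per-protocol sensitivity analysis, with a device-logged threshold fixed before unblinding. One example is 35 of the 42 daily sessions in each arm (6 weeks × 7 days, allowing one missed week). The documents do not dictate that value.

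The cost is a few sentences in 9.4.2 and 9.3. No new data are needed, since the device already logs use and a mixed model is already planned. The downside is that the all-randomised estimate may be smaller than the effect in full users, which the per-protocol analysis will show separately.

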#### 9.4.3 SAFETY ANALYSES

All AEs will be classified recorded and reported as noted in the Sections above.

#### 9.4.4 BASELINE DESCRIPTIVE STATISTICS

See statistical tests above. All analyzed metrics are computed for each subject's baseline.

#### 9.4.5 PLANNED INTERIM ANALYSES

N/A

#### 9.4.6 SUB-GROUP ANALYSES

N/A

#### 9.4.7 TABULATION OF INDIVIDUAL PARTICIPANT DATA

*State whether individual participant data will be listed by measure and time point.*

Individual data will be listed by time point.

#### 9.4.8 EXPLORATORY ANALYSES

*To be determined.*

### 10 SUPPORTING DOCUMENTATION AND OPERATIONAL CONSIDERATIONS

#### 10.1 REGULATORY, ETHICAL, AND STUDY OVERSIGHT CONSIDERATIONS

##### 10.1.1 INFORMED CONSENT PROCESS

###### 10.1.1.1 CONSENT/ASSENT AND OTHER INFORMATIONAL DOCUMENTS PROVIDED TO PARTICIPANTS

Consent forms describing in detail the study intervention, study procedures, and risks are given to the participant and written documentation of informed consent is required prior to starting intervention/administering study intervention.

###### 10.1.1.2 CONSENT PROCEDURES AND DOCUMENTATION

Informed consent is a process that is initiated prior to the individual's agreeing to participate in the study and continues throughout the individual's study participation. Consent forms will be Institutional Review Board (IRB)-approved and the participant will be asked to read and review

the document. The investigator will explain the research study to the participant and answer any questions that may arise. A verbal explanation will be provided in terms suited to the participant's comprehension of the purposes, procedures, and potential risks of the study and of their rights as research participants. Participants will have the opportunity to carefully review the written consent form and ask questions prior to signing. The participants should have the opportunity to discuss the study with their family or surrogates or think about it prior to agreeing to participate. The participant will sign the informed consent document prior to any procedures being done specifically for the study. Participants must be informed that participation is voluntary and that they may withdraw from the study at any time, without prejudice. A copy of the informed consent document will be given to the participants for their records. The informed consent process will be conducted and documented in the source document (including the date), and the form signed, before the participant undergoes any study-specific procedures. The rights and welfare of the participants will be protected by emphasizing to them that the quality of their medical care will not be adversely affected if they decline to participate in this study.

---

#### 10.1.2 STUDY DISCONTINUATION AND CLOSURE

This study may be temporarily suspended or prematurely terminated if there is sufficient reasonable cause. Written notification, documenting the reason for study suspension or termination, will be provided by the suspending or terminating party to investigator, and funding agency. If the study is prematurely terminated or suspended, the Principal Investigator (PI) will promptly inform study participants, the Institutional Review Board (IRB), and sponsor and will provide the reason(s) for the termination or suspension. Study participants will be contacted, as applicable, and be informed of changes to study visit schedule.

Circumstances that may warrant termination or suspension include, but are not limited to:

- Determination of unexpected, significant, or unacceptable risk to participants
- Demonstration of efficacy that would warrant stopping
- Insufficient compliance to protocol requirements
- Data that are not sufficiently complete and/or evaluable
- Determination that the primary endpoint has been met
- Determination of futility

Study may resume once concerns about safety, protocol compliance, and data quality are addressed, and satisfy the sponsor, IRB and/or Food and Drug Administration (FDA).

---

#### 10.1.3 CONFIDENTIALITY AND PRIVACY

Participant confidentiality and privacy is strictly held in trust by the participating investigators, their staff, and the sponsor(s) and their interventions. This confidentiality is extended to cover testing of biological samples and genetic tests in addition to the clinical information relating to participants. Therefore, the study protocol, documentation, data, and all other information

generated will be held in strict confidence. No information concerning the study or the data will be released to any unauthorized third party without prior written approval of the sponsor.

All research activities will be conducted in as private a setting as possible.

The ISM other authorized representatives of the sponsor, representatives of the Institutional Review Board (IRB), regulatory agencies or pharmaceutical company supplying study product may inspect all documents and records required to be maintained by the investigator, including but not limited to, medical records (office, clinic, or hospital) and pharmacy records for the participants in this study. The clinical study site will permit access to such records.

The study participant's contact information will be securely stored at each clinical site for internal use during the study. At the end of the study, all records will continue to be kept in a secure location for as long a period as dictated by the reviewing IRB, Institutional policies, or sponsor requirements.

Study participant research data, which is for purposes of statistical analysis and scientific reporting, will be transmitted to and stored with MICHR's REDCap Service (<https://www.michr.umich.edu/redcap-access>). This will not include the participant's contact or identifying information. Rather, individual participants and their research data will be identified by a unique study identification number. The study data entry and study management systems used by clinical sites and by MICHR's REDCap Service research staff will be secured and password protected. At the end of the study, all study databases will be de-identified and archived at the NIMH database.

#### 10.1.4 FUTURE USE OF STORED SPECIMENS AND DATA

Data collected for this study will be analyzed and stored with MICHR's REDCap Service. After the study is completed, the de-identified, archived data will be transmitted to and stored at the NIMH data repository for use by other researchers including those outside of the study. Permission to transmit data to the NIMH data repository will be included in the informed consent.

#### 10.1.6 SAFETY OVERSIGHT

Safety oversight will be under the direction of the PI and the ISM.

The ISM is independent from the study conduct and free of conflict of interest, or measures should be in place to minimize perceived conflict of interest. The ISM and PI will meet at least semiannually to assess safety and efficacy data on each arm of the study. The ISM will operate under the rules of an approved charter that will be written and reviewed at the organizational meeting of the ISM. At this time, each data element that the ISM needs to assess will be clearly defined. The ISM will provide its input to NIMH.

---

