## 4 STUDY DESIGN

### 4.1 OVERALL DESIGN

#### Aims/Hypotheses:

*Note: Aim 1 of the grant is to be performed in ANIMAL subjects only. However, Aim 2 of the grant is to be carried out in human subjects and therefore the design of Aim 2 is somewhat dependent on the results of Aim 1. For information purposes only, both are described below:*

**Specific Aim 1: Determine precise parameters/dosages for modulating multisensory plasticity in fusiform cells (FCs) and cartwheel cells (CWCs) in normal and pathological (tinnitus) circuitry in guinea pigs. Hypothesis 1: Presenting bimodal AN-SS stimuli with optimal parameters to guinea pigs with tinnitus will reverse pathological StDP in FCs and CWCs.**

**Specific Aim 2: Test parameters/dosages determined in Specific Aim 1, for modulation of multisensory plasticity in human subjects with changes in tinnitus severity as the outcome measure.** Hypothesis 2: AN-SS stimuli with optimal dosage/parameters (based on the results of Specific Aim 1), will effectively modulate DCN circuitry to reduce tinnitus in humans.

Experiment 2a: Using a double-blind cross-over model, we will use a bimodal AN-SS paradigm with optimal stimulus parameters based on the results of Specific Aim 1 to assess changes in subjects' tinnitus perception. Modulations in tinnitus perception will be assessed using objective loudness matching and subjective measures (standard questionnaires) in response to active and sham bimodal stimuli. Neural circuitry changes will be assessed by examining changes in the severity of subjects' tinnitus. It is anticipated that chosen bimodal intervals and durations of treatment (dose) will reduce the abnormal percepts. Experiment 2b: Subjects will

be monitored during a washout period for a return to baseline to determine durability of effect. To assess dose-response of the bimodal modulation, the length of bimodal stimulation treatment will be varied and effects and duration of effect on tinnitus will be assessed as above

**Phase:** Phase I/II

**Type of design:** Double-blinded, cross-over design. There will be two treatment arms (treatment and sham). All subjects will participate in both arms of the study. This is a single-site study. Total duration of the study for each subject will be 36 weeks.

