## 8.2 SAFETY AND OTHER ASSESSMENTS

Subject participation will entail weekly visits to the lab for detailed assessments. The weekly visits to the lab will ensure that subjects are using the devices correctly and safely. The weekly visits also allow us to monitor changes in the tinnitus percept in response to device use or washout from the treatment. The regular assessments also provide us with the opportunity to detect any adverse events as soon as possible, should any occur.

Currently, there is no standard treatment for tinnitus that has been shown to be broadly effective at treating tinnitus, so participation in the study will not interfere with standard clinical intervention. Subjects will be informed during the consenting process that there are alternative methods of treatment such as sound therapy that they may find beneficial, and

referred to their primary care physician for referrals should they elect to pursue that form of treatment.

Regular assessments will also allow for swift intervention should a subject experience an adverse event or worsening of symptoms. We will stop the study should 10% of subjects show a persistent worsening in their symptoms. A subject's participation in the study will be discontinued following **both** 1) an increase of 16 or more points in TFI, **and** 2) an average increase of 12 dB in TinnTester compared to baseline, for two consecutive weekly measures. Both measures are our primary outcome measures. Using both criteria for determining discontinuation is critical as the tinntester measures tinnitus loudness, which reflects the circuitry changes identified in our preclinical studies. TFI is also important for the human study as it gauges the subject's subjective response to their tinnitus. However, TFI can also reflect outside life stressors unrelated to the treatment and could result in a subject's discontinuation for reasons unrelated to the treatment. A subject's participation can also be discontinued even if the criteria above is not met, but the subject feels their tinnitus is worse.

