This study does not require and will not use a Data Safety Monitoring Board (DSMB) because it is not a multi-site study. However, because it is a double-blinded, cross-over study we will implement and an Independent Safety Monitor (ISM) for data monitoring purposes. *The ISM will be clinical research monitor of the Michigan Institute for Clinical & Health Research (MICHR) who can provide independent monitoring of the human data. The ISM will be responsible for overseeing and monitoring the enrollment data, safety data and data integrity. The ISM will be unblinded to the intervention assignment for each subject. The ISM will be independent of the investigation. He/she will not be a collaborator, co-author, supervisor, mentor/mentee, research lab member, or member of the institutional department within the last three years. He/she will not have any professional or financial conflict of interest.*

The PI ([name]) will comply with the NIMH Reportable Events policy. The intervention will continue for each subject so long as adverse events do not occur for that individual. The ISM will monitor data and review safety data. If adverse events related to the study (definitely related, probably related, or potentially related) do occur, they will be reported to the IRB within 14 days and will be reported to the PI immediately. All other adverse events will be reported annually at the time of IRB renewal. This study uses a non-invasive device. We will use strictly calibrated instruments to ensure that both acoustic and electrical stimulation are being delivered at safe levels for each subject. However, specific stopping rules will be identified for each subject to ensure patient safety. For each subject, data for the TFI, THI, TinnTester, and audiologic examinations will be examined on a weekly basis (following weekly testing for each subject) for tinnitus assessments to determine if either measures indicate a statistically significant increase in tinnitus or decrease in hearing (in reference to the individual's baseline measure). This metric will be monitored by the ISM. If tinnitus is found to increase or hearing loss worsen, then the subject will not continue in the study regardless of which arm (active or sham) in which the subject is enrolled. Furthermore, if the subject subjectively reports increase in tinnitus or worsening of hearing, without a significant change in

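### Interim analyses are listed as N/A (9.4.5), yet the PI and the unblinded safety monitor are to review efficacy data by arm at least twice a year (10.1.6), and efficacy is a ground for stopping with no boundary (10.1.2)

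*Combined protocol and SAP*

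**What the plan says.** All references are to the combined protocol and SAP.

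- The section headed "9.4.5 PLANNED INTERIM ANALYSES" contains only N/A. Section 9.4.1 places the final analysis after unblinding.
- Section 10.1.6: "The ISM and PI will meet at least semiannually to assess safety and efficacy data on each arm of the study". It adds that the ISM will work under a charter still to be written, in which the data elements to be assessed will be defined, and that the ISM gives input to NIMH.
- Section 8.2: "The ISM will be unblinded to the intervention assignment for each subject".
- Section 10.1.2 lists circumstances that may warrant suspension or termination. Two of them are "Demonstration of efficacy that would warrant stopping" and "Determination that the primary endpoint has been met". Futility is also listed. None has a threshold.
- Section 4.2 requires all study team members to be blinded. Section 6.3 names two occasions for unblinding, the end of the study and an SAE related to the study, and says that no investigator may remain unblinded. It also allows investigators who have no contact with subjects to unblind.
- Section 9.4 sets a two-sided alpha of 0.05 for all hypothesis tests.

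No efficacy boundary, alpha-spending rule or number of looks appears anywhere.

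**The concern.** The statistical section says there is no interim look. The oversight section schedules a recurring one on efficacy data, attended by the PI, and the closure section lets efficacy end the trial. A study team cannot follow all three.

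Two things are at stake. The first is blinding. A PI who sees active and sham outcomes during the trial knows the emerging difference while 9.3 still leaves the per-protocol set and the handling of outliers undefined, so those choices could be made with knowledge of the results. The second is error control. A review that can stop the trial for efficacy at the unadjusted 0.05 level adds chances of a false positive, and the plan makes no allowance for this.

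The ISM's own access to outcome data is not a fault. Section 8.2 has the ISM follow worsening on TFI, THI and TinnTester ("This metric will be monitored by the ISM"), and it says of TFI and TinnTester that "Both measures are our primary outcome measures". Safety monitoring cannot avoid these measures.

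**Working it through.** **Step 1: what *arm* means in 10.1.6.**

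- Used for treatment condition: the synopsis (1.1), on treatment durations, glosses the arms as treatment and sham. Sections 7.1 and 8.2 gloss *arm* as active or sham when discussing discontinuation. Section 4.1 says "There will be two treatment arms (treatment and sham".
- Used for period: the schedule in 1.3, and 6.1.2 and 7.3, where Arm 1 and Arm 2 are the first and second six-week periods with their washouts.

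Three sections besides 8.2 define the word explicitly as treatment versus sham, so that reading is favored, but 10.1.6 does not settle it. On the treatment reading the PI sees results by condition. On the period reading the PI sees Arm 1 and Arm 2 data with the two sequences mixed and is not unblinded.

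**Step 2: the treatment reading against the blinding rules.** Section 4.2 blinds the whole team. A semiannual meeting is neither of the two occasions named in 6.3. The allowance in 6.3 for investigators without subject contact could cover the PI, but the documents do not say whether the PI has such contact.

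**Step 3: type I error, if a look can stop the trial.**

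Inputs: two-sided alpha 0.05, critical value 1.96 (9.4); meetings at least every six months (10.1.6); study duration 4 years (1.1). The number of looks K is not given. An illustrative upper case is 4 years × 2 per year = 8, with the last meeting coinciding with the final analysis. Because meetings are *at least* semiannual, this is not a bound.

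Formula, for one endpoint under no effect with equally spaced information: Z_k = (X_1 + … + X_k)/√k, with independent standard normal X. The overall error is P(|Z_k| > 1.96 for at least one k from 1 to K). Numerical integration, confirmed by simulation, gives:

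- K = 1 (the plan's own position): 5.0%
- K = 2: 8.3%
- K = 4: 12.6%
- K = 8: 17.6%

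These count a stop in either direction. Interim stops for benefit only would give less. With no efficacy stop the rate is 5.0% however many meetings are held, and stopping for futility alone does not raise it.

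**The case against.** The strongest reply is that nothing here amounts to an interim analysis. Section 10.1.2 is a permissive list, no passage links it to the 10.1.6 meetings, no test is specified at those meetings, and neither the ISM nor the PI is given authority to stop for efficacy. Section 10.1.6 is headed as safety oversight, and efficacy data may simply mean TFI, THI and TinnTester watched for worsening. A stopping rule could still be placed in the charter.

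Much of this stands. A reader might infer that the trial's false positive rate is inflated to some definite figure. The documents do not support that: the inflation occurs only if a review can stop the trial on a test that the text never describes. Nor do they support deriving exact looks from the planned accrual rate. The summary of changes and the amendment history (10.4) report incomplete data after the pandemic shutdown and present the 100 randomized subjects as a ceiling for reaching 50 with complete data. The mixed model in 9.4.1 would also use partly observed subjects.

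A reader might also infer that the PI is certainly unblinded. That depends on the reading of *arm* and, under 6.3, on whether the PI has contact with subjects.

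What does not stand is the view that no change is needed. If only worsening is meant, the text should say so. The charter is promised to cover operating rules and data elements, not a boundary or a limit on what the PI sees. Permissive or not, the two efficacy grounds sit in the protocol with no threshold.

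**Conclusion.** The text is wrong as written: 9.4.5, 10.1.6 and 10.1.2 cannot all be followed, and on the favored reading of *arm*, 10.1.6 also conflicts with 4.2 and with the unblinding occasions in 6.3. This conclusion rests on the wording alone and is firm.

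The size of the statistical consequence is conditional. It is nil (5.0%) if no review can stop the trial for efficacy. It is about 8% to 18% for two to eight equally spaced looks, if each could stop the trial at an unadjusted two-sided 0.05 on one endpoint. The number and spacing of looks are assumptions. The plan should be corrected, but the documents do not show that an unadjusted stop is intended.

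**What to change.** Reconcile 9.4.5, 10.1.6, 10.1.2 and 6.3.

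- **10.1.6:** state that the joint ISM–PI meetings review enrollment, data integrity and safety data pooled over treatment condition. Data by treatment condition (active or sham) are seen only by the unblinded ISM, for safety, including worsening on TFI, THI and TinnTester. No active-versus-sham efficacy comparison is made before database lock. Carry this into the ISM charter.
- **9.4.5:** replace N/A with *None planned; see 10.1.6*.
- **10.1.2:** delete the demonstrated-efficacy and primary-endpoint-met grounds.
- Leave every safety rule unchanged, and the SAE unblinding in 6.3 with them.

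If early efficacy stopping is wanted, 9.4.5 must instead prespecify the number and timing of looks, the endpoint tested and an alpha-spending boundary, with review that excludes the PI. The effect on sample size is small. Section 9.2 requires 2 × 17 = 34. For two to eight looks at 80% power, O'Brien-Fleming inflation of 1.008 to 1.037 gives 17.1 to 17.6, so 18 per arm and 36 in total. Pocock inflation of 1.110 to 1.279 gives 18.9 to 21.7, so 19 to 22 per arm and 38 to 44 in total. Both are within the planned minimum of 50. They are approximate, because 9.2 rests on 50 simulations per sample size and gives no slopes or SDs from which to re-derive the 17.

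The cost is otherwise wording. The PI loses any by-treatment view before lock, and an early efficacy stop that 9.4.5 never planned is lost. The amendment history (10.4, version 1.4) says the monitor is not a medical monitor, so the charter should state how a by-treatment safety concern reaches a clinician, using the existing route in 6.3.
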